**A. Study Title:**

Can proprioceptive knee brace improve functional outcome following total knee arthroplasty?

**B. Introduction:**

Osteoarthritis is among the most prevalent form of degenerative joint disease in arthritis (1). The World Health Organisation identified osteoarthritis as one of the top ten most disabling cause of disease in developed countries (2), and the single most common cause of disability for elderly persons (3). In fact, worldwide statistics for men and women over 60 years of age with signs of symptomatic osteoarthritis are estimated to be at 9.6% and 18.0% respectively (2). In Hong Kong, the latest census revealed that 514,000 people suffer from degenerative arthritis, representing 0.7% of the population (4). Although these values are much lower than the international figures reported by the WHO, it is inevitable that the prevalence of osteoarthritis will continue to rise with an increasing trend of obesity and an aging population in Hong Kong (5, 6). Similar to any other chronic disease with wide prevalence, the impact of osteoarthritis translates to a substantial socioeconomic burden on a societal level.

Total knee arthroplasty has become the gold standard to manage the pain and disability associated with end-stage arthritis who have exhausted all conservative measures. Although contemporary advances in prosthesis design, surgical techniques, postoperative rehabilitation regimes have hasten patient's recovery, the restoration of proprioception and neuromuscular control is often prolonged despite solid rehabilitation regimes(7, 8) .

Knee bracing is one of the non-pharmacological modalities designed to evenly distribute load and provide proprioceptive feedbacks for those with knee injuries or knee pain (9-11). There are four categories of knee braces for the purpose of prophylactic, functional, rehabilitative and unloader/off-load. This study will mainly be focusing on the effects of the unloader/off-loader brace. Previous studies have demonstrated the effects on alteration of kinematic variables, including range of movement ( $p=0.002$ ), speed of walking ( $p<0.001$ ) and knee adduction moment ( $p=0.001$ ) for knee injuries and osteoarthritis (12, 13) as a part of the conservative management protocol. However, there have few studies (14) that investigated whether proprioceptive knee bracing has any role in functional recovery post total knee arthroplasty.

**C. Aims and Hypotheses to be tested:**

This proposed research study aims to conduct a randomised control trial to evaluate the functional outcomes of the utilisation of proprioceptive knee brace following total knee arthroplasty.

**D. Description of the knee unloader brace:**

For the intervention group that randomly consisted of 15 subjects will be using a design of knee brace (Reaction Web®; DonJoy, Vista, CA). The elastomeric web design helps to reduce pain by dispersing load across the knee. The web acts like a spring to absorb shock and shifts the peak loads away from the painful area of the knee. Elastomeric web acts to dynamically stabilise the patella on all sides, bringing the patella into proper tracking position to reduce pain for patients with general patellofemoral instabilities. Reaction Web® has dual-axis hinges that are flexible, creating synergy with the elastomeric web for optimal fit and support, and providing energy dispersion to the knee.

(The above information was retrieved from DonJoy website)

**E. Plan of Investigation:**

30 patients with end stage knee OA who are schedule for TKA will be recruited via face to face promotion from the Li Ka Shing Orthopaedics Specialist clinic at the Department of Orthopaedics and Traumatology at Prince of Wales Hospital (PWH) Hong Kong. 15 patients will be randomly allocated to each of the treatment (proprioceptive knee brace + routine post-operative procedures) and control (routine post-operative procedures) groups.

Part 1a. Preliminary assessment on patients from Prince of Wales Hospital Orthopaedics specialist clinic based on inclusion and exclusion criteria

Part 1b. Preliminary assessment on patients [i.e. Basic demographics, Knee Function Assessment, Outcome Measurement Questionnaires]

Part 1c. Randomise allocation between treatment and control group

Part 2. Peri-operative assessment [i.e. Length of Hospital Stay]

Part 3. Distribution of knee brace (available to treatment arm) post-operative 2 to 4 week recovery

Part 4a. Post-operative 6 weeks Assessment

Part 4b. Post-operative 6 months Assessment

Part 4c. Post-operative 12 months Assessment

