**F. Methods:**

**(1) Post recruitment assessment**

After recruitment, oral and written consents will be obtained from individuals who agree to participate in the study. The recruitment period will last for 12 months and the whole project period is 2 years in total. Basic Demographics, Knee Function Assessment and Physical Activity Questionnaires will be carried out.

Inclusion criteria - Patients are included in the experiment if

- (1) Adult (age over 18 years old) underwent Total Knee Arthroplasty within 2 to 4 weeks;
- (2) Adult who is able to provide written consent and compliance with treatment and assessment regime

Exclusion criteria - Patients are excluded from the experiment if

- (3) Patients with disabilities, wheelchair dependence for mobility;
- (4) Underwent revision Total Knee Arthroplasty;
- (5) Found with complication wounds following surgery;
- (6) Diagnosed with comorbidities e.g. inflammatory arthritis, obesity, dermatological disorders that might affect their compliance to treatment;
- (7) Do not fit to the sizes of knee braces;
- (8) Not to give written consent and be non-compliance with the treatment and assessment regime

Sample Size Estimation

The sample size estimation was calculated using GPower 3.1 based on the yearly admission total knee replacement cases at Prince of Wales hospital. Effect size was calculated at 0.5. With 95% power and an alpha value of 0.05, 12 participants are required for each of the study control and intervention groups. An additional 25% will be added to account for possible attrition. Total 30 (15x2) subjects will be recruited for this study.

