### Basic Demographics

Pre-operation baseline demographics will be collected for inter-patient comparisons:

1. Gender
2. Age
3. Height, Weight and Body Mass Index
4. Duration of Symptomatic Knee OA
5. Ethnicity

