### 4. Knee Society Score (KSS), Knee Society Function Score (KFS)

The KSS is an instrument assessing patient's pain and functionality based on a series of questions interviewed by a clinician. The validated questionnaire combines the objective physician derived component with a subjective patient derived component which evaluates pain, functionality, satisfaction and fulfillment of expectations. The results will be calculating the total score with 100 being the highest and 0 the lowest.

Physical Assessments	Prep-op	6 weeks	6 months	12 months
----------------------	---------	---------	----------	-----------

6m gait	✓	✓	✓	✓
TUG	✓	✓	✓	✓
Active ROM	✓	✓	✓	✓
KT-1000	✓	✓	✓	✓
Knee extensor/flexor	✓	✓	✓	✓
SF12	✓	✓	✓	✓
WOMAC	✓	✓	✓	✓
KSS & KFS	✓	✓	✓	✓
Compliance assessment	✓	✓	✓	✓
Satisfaction Survey	✓	✓	✓	✓

**Clinical Research Compliance assessment** will be conducted to measures the period and amount of time designated knee brace has been put on as interventional means. It is also recorded to the attendance of routine post-operative procedures of physiotherapy training one might receive.

**Patients satisfaction Survey** is to be recorded in terms not only how well to the quality of care patient was being treated, but to also the content a patient is with the care they received.

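### Randomisation is listed before surgery although the brace is given only 2 to 4 weeks after it, with no concealment described in between and eligibility criteria that contradict the order

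*Protocol*

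**What the plan says.** Section E (Plan of Investigation) sets the sequence. Recruitment is before surgery: "30 patients with end stage knee OA who are schedule for TKA will be recruited via face to face promotion". After screening (1a) and preliminary assessment (1b) comes "Part 1c. Randomise allocation between treatment and control group". Next is "Part 2. Peri-operative assessment [i.e. Length of Hospital Stay", and then the hand-out: "Part 3. Distribution of knee brace (available to treatment arm) post-operative 2 to 4 week recovery". The first outcome visit (Part 4a) is 6 weeks after surgery. The same section defines the arms as routine post-operative procedures with or without the brace. Basic Demographics places the baseline before surgery: "Pre-operation baseline demographics will be collected for inter-patient comparisons".

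Section F, (1) Post recruitment assessment, points the other way. The first inclusion criterion reads "1) Adult (age over 18 years old) underwent Total Knee Arthroplasty within 2 to 4 weeks", and one exclusion is "5) Found with complication wounds following surgery". Neither can be judged in a patient who is still waiting for the operation.

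The protocol does not say when the allocation is disclosed or to whom, and it describes no concealment or masking. The assessment table and the statistical analysis section list four time points: pre-operative, 6 weeks, 6 months and 12 months. None falls between surgery and hand-out.

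**The concern.** A randomised comparison is cleanest when allocation happens just before the treatments diverge. Here they diverge at Part 3, but allocation is listed two steps earlier, with the operation, the hospital stay and the first weeks of rehabilitation in between. If the arm becomes known during that time, ward staff, physiotherapists and patients can act on it. The primary outcome is speed and range of motion, measured by timed walking, the timed up-and-go test and active knee movement. These depend on effort and could respond to differences in early rehabilitation.

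Two things are at stake. First, a difference that arises before the brace would enter the 6-week comparison and, with no assessment just before hand-out, could not be separated from a brace effect. Second, patients who withdraw, or who turn out to have a wound complication, after randomisation but before hand-out become post-randomisation losses that never had the chance to receive the treatment. They cause missing data or selection, and they draw on a small attrition allowance.

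**Working it through.** The plan gives no figure for this point. The check is a reading of the sequence, followed by one illustrative calculation.

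**Sequence under each reading**

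| Step | Section E order | Section F criteria applied literally |
|---|---|---|
| Screening (1a) | before surgery | 2 to 4 weeks after surgery |
| Baseline (1b) | before surgery | conflicts with the pre-operative baseline |
| Randomisation (1c) | before surgery | about the time of hand-out |
| Hand-out (Part 3) | 2 to 4 weeks after surgery | 2 to 4 weeks after surgery |
| Gap from randomisation to brace | at least 2 to 4 weeks, including surgery | little or none |

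Part 1a says screening uses the inclusion and exclusion criteria, and it precedes 1c. The two sections therefore cannot both be followed. The exposure exists under the section E order and largely disappears under the section F reading. It would persist if the conflict were settled by making every criterion pre-operative and leaving 1c where it is.

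**Share of the first follow-up interval before the brace**

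Inputs: hand-out at 2 to 4 weeks and first outcome visit at 6 weeks (section E).

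- Earliest hand-out: 2/6 = 33%.
- Latest hand-out: 4/6 = 67%.

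This is elapsed time, not bias. It shows only why the 6-week visit is the most exposed.

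**Attrition allowance**

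The sample size paragraph needs 12 per arm and adds 25%: 12 × 1.25 = 15. The allowance is 15 − 12 = 3 patients per arm for the whole 12 months. Any loss between randomisation and hand-out comes out of those 3.

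**Illustration of a pre-brace difference**

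The documents give no size for such a difference, so a range of 0.2 to 0.4 SD is assumed. The setting is no brace effect and one unadjusted two-sided 5% t-test at 6 weeks. With n per arm and shift b in SD units, the noncentrality is b × √(n/2) on 2n − 2 degrees of freedom.

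| Assumed shift b | Noncentrality, n = 15 (28 df) | Rejection, n = 15 | Rejection, n = 12 (22 df) |
|---|---|---|---|
| 0.2 SD | 0.2 × √7.5 = 0.55 | 8.3% | 7.6% |
| 0.3 SD | 0.3 × √7.5 = 0.82 | 12.5% | 10.8% |
| 0.4 SD | 0.4 × √7.5 = 1.10 | 18.5% | 15.5% |

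Without a shift the rate is 5%.

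**The case against.** A reader might infer that the arm is revealed before surgery and that surgery and early care run with it known. The text does not say so. Part 1c says only that allocation is randomised there. An allocation drawn at 1c could be kept sealed until Part 3 without contradicting anything written. What stands is narrower: the protocol describes nothing that would keep it hidden.

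A reader might also take pre-operative randomisation as settled. It is not, because inclusion criterion 1 and exclusion criterion 5 imply eligibility after surgery. On that reading the gap closes and what remains is a contradiction to reconcile. This limits the point but does not remove it: section E is the only place that sets the order of steps, and the pre-operative baseline agrees with it.

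The illustration is open to challenge too. It models one t-test at one visit, whereas the plan is an ANOVA over four time points, and a brief early difference may fade by 6 and 12 months. No document supports any particular shift.

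Physiotherapy attendance is to be recorded ("It is also recorded to the attendance of routine post-operative procedures of physiotherapy training one might receive"), so one route of bias would be partly visible, though not prevented. Finally, the control arm has no sham brace. Patients and therapists will know the arm from hand-out onwards whatever is done, so later randomisation removes only the part of the problem that precedes hand-out.

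**Conclusion.** The point holds as a weakness in the order of steps together with a contradiction between sections E and F. As listed in section E, randomisation comes at least 2 to 4 weeks before the treatments differ, with no concealment described and no assessment in between. This permits arm-dependent early care, effort and withdrawal, and loss or ineligibility after randomisation but before treatment. It bears mainly on the 6-week comparison, where 33% to 67% of the interval precedes the brace.

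The size of any bias is unknown. The 8% to 18% range rests wholly on the assumed 0.2 to 0.4 SD shift and a single 6-week t-test. It should not be read as the trial's expected error rate. Nor do the documents show that the arm is disclosed early or that care will in fact differ; these are risks the plan leaves open. This is an improvement worth making because it is cheap, not a defect that invalidates the design. When patients are allocated is trial conduct that the protocol itself sets, so it is not a detail left to a statistical analysis plan.

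**What to change.** Keep consent, demographics and baseline assessment before surgery. Move Part 1c to the Part 3 contact and randomise there, once eligibility has been confirmed. Reconcile section F with this order by stating which criteria are checked before surgery and which at the 2 to 4 week contact. Report the number lost between consent and randomisation, with reasons, separately from post-randomisation losses.

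Generating the allocation at Part 3 is better than drawing it at 1c and keeping it sealed. Under sealing, patients lost before opening already belong to an arm, can differ between arms by chance, and can upset the 15 and 15 split, so a rule for the analysis population and for replacement would be needed. If the sponsor prefers to keep randomisation at 1c, the protocol should at least state that the allocation stays concealed from patients and staff until Part 3.

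Cost: edits to sections E and F, with no added visit or patient procedure. Brace sizes must be in stock before the arm is known, and slightly more patients may have to be consented to randomise 30. The change does not address knowledge of the arm after hand-out.

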**F. Methods:**

**(1) Post recruitment assessment**

After recruitment, oral and written consents will be obtained from individuals who agree to participate in the study. The recruitment period will last for 12 months and the whole project period is 2 years in total. Basic Demographics, Knee Function Assessment and Physical Activity Questionnaires will be carried out.

Inclusion criteria - Patients are included in the experiment if

- (1) Adult (age over 18 years old) underwent Total Knee Arthroplasty within 2 to 4 weeks;
- (2) Adult who is able to provide written consent and compliance with treatment and assessment regime

Exclusion criteria - Patients are excluded from the experiment if

- (3) Patients with disabilities, wheelchair dependence for mobility;
- (4) Underwent revision Total Knee Arthroplasty;
- (5) Found with complication wounds following surgery;
- (6) Diagnosed with comorbidities e.g. inflammatory arthritis, obesity, dermatological disorders that might affect their compliance to treatment;
- (7) Do not fit to the sizes of knee braces;
- (8) Not to give written consent and be non-compliance with the treatment and assessment regime

Sample Size Estimation

The sample size estimation was calculated using GPower 3.1 based on the yearly admission total knee replacement cases at Prince of Wales hospital. Effect size was calculated at 0.5. With 95% power and an alpha value of 0.05, 12 participants are required for each of the study control and intervention groups. An additional 25% will be added to account for possible attrition. Total 30 (15x2) subjects will be recruited for this study.

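### Does exclusion criterion (8) allow randomised patients to be removed for not complying?

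*Protocol*

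**What the plan says.** Protocol section F, (1) Post recruitment assessment, opens its exclusion list with "Exclusion criteria - Patients are excluded from the experiment if". Item (8) of that list is "Not to give written consent and be non-compliance with the treatment and assessment regime". Its counterpart is inclusion criterion (2): "Adult who is able to provide written consent and compliance with treatment and assessment regime".

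The same section says of consent: "After recruitment, oral and written consents will be obtained from individuals who agree to participate in the study". Exclusion (6) concerns comorbidities "that might affect their compliance to treatment", which is a forward-looking judgement.

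Section E, Plan of Investigation, applies the inclusion and exclusion criteria in Part 1a, randomises in Part 1c and hands out the brace, to the treatment arm only, in Part 3. The schedule table ticks a compliance assessment at all four time points. The note below it says that brace wear and physiotherapy attendance are recorded. Data Processing and Statistical Analysis compares the treatment and control groups by ANOVA.

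**The concern.** Two things look wrong.

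**The conjunction.** Inclusion (2) demands consent and compliance together, so its negation is the absence of either one. Item (8) names only the patient who lacks both. Because consent is obtained from everyone who takes part, no consented patient could ever meet (8) as literally written.

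**The timing.** Item (8) speaks of being non-compliant, not of being expected to be, and gives no time of judgement. Actual failure to wear the brace can be seen only after Part 3, which follows randomisation. Nor can one say that every item in the lists is settled before surgery: inclusion (1), "underwent Total Knee Arthroplasty within 2 to 4 weeks", and exclusion (5), "Found with complication wounds following surgery", both need the operation to have taken place.

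If staff took (8) as permission to remove patients during follow-up, removals for low brace wear could come only from the brace arm. The groups compared would then no longer be the groups randomised. They are also small. The plan has 12 per arm and says "An additional 25% will be added to account for possible attrition", so 12 × 1.25 = 15 and the allowance is 15 − 12 = 3 per arm. Each removal would use a third of it.

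**Working it through.** **1. Does the conjunction change who enters?** Take each combination of consent and compliance. A patient enters if inclusion (2) is met and exclusion (8) is not.

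| Consents | Will comply | Meets inclusion (2) | Hit by (8) as written | Hit by (8) with 'or' | Enters, as written | Enters, with 'or' |
|---|---|---|---|---|---|---|
| yes | yes | yes | no | no | yes | yes |
| yes | no | no | no | yes | no | no |
| no | yes | no | no | yes | no | no |
| no | no | no | yes | yes | no | no |

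Item (8) fails to mirror inclusion (2) in two of the four rows, yet the last two columns are identical. The table takes inclusion (2) to cover willingness as well as ability. A patient who could consent but declines is in any case stopped by the consent step, which enrols only those who agree.

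**2. Which reading of the timing does the text support?**

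- The lead-in to the exclusion list is the mirror image of the lead-in to the inclusion list, which uses the same sentence for inclusion. It is an ordinary eligibility heading, not a withdrawal rule.
- Item (8) uses the same terms for the regime as inclusion (2), and it begins with refusal of consent, which is a matter of entry.
- Section E places the check of the criteria (Part 1a) before allocation (Part 1c).
- Exclusion (6) treats compliance as something to be foreseen.
- The compliance assessment runs to 12 months and has no cut-off and no consequence. That suits a study that keeps its poor compliers.
- The analysis section does not restrict the comparison to compliers.

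Inclusion (1) and exclusion (5) show that Part 1a alone does not settle the timing of every item. They concern the operation and the wound, however, and do not carry (8) past the distribution of the brace. No sentence in the protocol says that a randomised patient will be removed for low wear.

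**3. What would be at stake if removals did occur?** The protocol gives no figures for this. The following are assumptions: no true effect, 15 per arm, standard normal wear, a correlation r between wear and outcome, and the k lowest wearers removed from the brace arm only. Then

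shift = r × (mean wear of those kept).

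The three lowest expected order statistics for n = 15 are −1.7359, −1.2479 and −0.9477.

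| k | Mean wear of those kept | Shift at r = 0 | at \|r\| = 0.3 | at \|r\| = 0.5 |
|---|---|---|---|---|
| 1 | 1.7359/14 = 0.124 | 0 | 0.04 SD | 0.06 SD |
| 2 | 2.9838/13 = 0.230 | 0 | 0.07 SD | 0.11 SD |
| 3 | 3.9315/12 = 0.328 | 0 | 0.10 SD | 0.16 SD |

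Simulation of a single pooled t-test under the same assumptions gives a two-sided error of at most 5.8% at |r| = 0.3 and 7.3% at |r| = 0.5, against a nominal 5%. If the same ground removed three from each arm equally, the shift would be 0. If (8) is a screening item, or is taken literally, the shift is also 0.

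**The case for a change.** The best case for acting is that the remedy costs almost nothing. One word and a phrase fixing the time of judgement would close a reading that, if adopted, breaks the randomised comparison in a trial of 30. Eligibility wording belongs to the protocol, and an analysis plan would not normally correct it. The present wording does describe conduct rather than expectation.

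Part of this stands: (8) is badly drafted, and an editor could tidy it at the next amendment. But a cheap edit is worth requiring only if something turns on it. The change of conjunction alters no enrolment. The harmful reading needs staff to treat an eligibility item as a withdrawal rule, and nothing in the text directs them to. A statement that low compliers stay in the comparison by allocated group would be a definition of the analysis population, which is commonly left to the statistical analysis plan. That plan is not shown, so its content cannot be held against the protocol.

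The order of events is a different matter. Section E recruits patients scheduled for surgery and lists randomisation before the peri-operative stage, while inclusion (1) and exclusion (5) can be judged only afterwards. That conflict is real and those sections need to be reconciled. It concerns other criteria, though, and lends no weight to this point.

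**Conclusion.** No change to the plan follows. Criterion (8) is a clerical slip in an item that duplicates inclusion (2). Correcting it would alter the entry decision in none of the four possible cases, and it would leave the comparison of the two groups as it is.

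This rests on two assumptions: that screeners read ability to comply as including willingness, and that (8) is applied as the eligibility item it appears to be. If the first failed, a consenting but unwilling patient might be randomised. Such a patient would still be followed and compared by group, so the randomisation would be intact. If the second failed, the shift would depend on how many were removed, from which arm, and how wear relates to outcome, none of which the protocol gives. The 0.16 SD figure is illustrative and does not measure a defect in the plan.

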#### **Data Processing and Statistical Analysis:**

Demographic characteristics will be demonstrated using Student t-test or Chi-square test for continuous data and categorical data respectively where appropriate. The accuracy of primary measurements between the treatment (proprioceptive knee brace + routine post-operative procedures) and control (routine post-operative procedures) groups at the 4 time points (Pre-operative, 6 weeks, 6 months, 12 months) will be compared using ANOVA. Secondary outcomes and different types of patient-oriented quality of life questionnaires collected at the 4 time points will be compared using ANOVA likewise. All statistical analysis will be carried out using IBM SPSS version 25 (Armonk, NY:IBM Corp).

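### The stated effect size of 0.5, alpha 0.05 and 95% power do not lead to 12 patients per group; read as a 0.5 SD difference at one visit they require 105, and 12 gives 21.6% power

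*Protocol*

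**What the plan says.** In the protocol, section F (Methods), Sample Size Estimation, the calculation is attributed to G*Power 3.1 and described as "based on the yearly admission total knee replacement cases at Prince of Wales hospital". The target is given as "Effect size was calculated at 0.5", followed by "With 95% power and an alpha value of 0.05, 12 participants are required for each of the study control and intervention groups". A quarter is then added for attrition (12 × 1.25 = 15 per group), giving "Total 30 (15x2) subjects will be recruited for this study".

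The Data Processing and Statistical Analysis section plans that the primary measurements of the two "groups at the 4 time points (Pre-operative, 6 weeks, 6 months, 12 months) will be compared using ANOVA". It does not say whether the group effect, the group-by-time interaction or a visit-by-visit comparison is the test of interest, and it does not link that test to the sample size. The primary outcome is listed as speed and range of motion of the knee, without one measure or one visit.

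**The concern.** The paragraph reads as a finished derivation: three inputs and a result. A reader will take it to mean that the trial has only a 5% chance of missing an effect of 0.5. In a two-group comparison, 0.5 is most readily taken as half a standard deviation, and 12 per group is far too few for that at 95% power. The one stated basis, an annual count of knee replacements, can show that recruitment is feasible but cannot supply a standardised effect.

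At stake is how the result will be read. If the real target is 0.5 SD and the true power is near 20%, a null finding would be the likely outcome even if the brace works. With 95% power on record, that finding would be taken as good evidence of no benefit.

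**Working it through.** **Inputs from the protocol.** Effect size 0.5 (metric not given); alpha 0.05 (sidedness not given); power 95%; 12 per group, 24 in total; 15 per group, 30 in total, after attrition; ANOVA over four time points. Correlations and visit counts other than four are assumptions made here.

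**1. Two groups at one visit, d = 0.5.** Noncentral t with 2n − 2 degrees of freedom and noncentrality d·√(n/2).
- n = 12: 0.5 × √6 = 1.22 on 22 df. Power is 21.6% two-sided, 32.4% one-sided.
- n = 15: power is 26.2% two-sided, 37.9% one-sided.
- n = 104 gives 94.8% and n = 105 gives 95.0%, so 105 per group two-sided. One-sided, 88 per group.
- With 12 per group, two-sided, 95% power is reached at 1.54 SD and 80% at 1.20 SD. With 15 per group the figures are 1.36 and 1.06 SD.

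**2. Two groups, Cohen's f = 0.5.** With two equal groups f = d/2, so d = 1.0. This needs 27 per group; 12 per group gives 64.9%.

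**3. Repeated-measures ANOVA.** Two groups, m visits, total N, correlation ρ, compound symmetry and sphericity assumed.
- Between-group: λ = f²·N·m / (1 + (m − 1)ρ), df 1 and N − 2.
- Group-by-time: λ = f²·N·m / (1 − ρ), df m − 1 and (m − 1)(N − 2).

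With f = 0.5, m = 4, ρ = 0.5:
- Between-group: N = 36 (λ = 0.25 × 36 × 4 / 2.5 = 14.4). N = 24 gives 84.2%.
- Group-by-time: N = 12 (λ = 0.25 × 12 × 4 / 0.5 = 24), that is 12 in total, not per group.

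**4. Settings that do return N = 24.** The implied difference follows from f = d/2 for the between-group effect. For group-by-time, a constant shift Δ after surgery with none at baseline gives f = (Δ/2)·√(m − 1)/m.

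| Effect | f | Visits | ρ | Power at N = 24 | Implied difference |
|---|---|---|---|---|---|
| Between-group | 0.5 | 4 | 0.2 | 95.9% | 1.0 SD at every visit |
| Between-group | 0.5 | 3 | 0.1 | 95.9% | 1.0 SD at every visit |
| Group-by-time | 0.5 | 3 | 0 | 96.5% | 2.12 SD |
| Group-by-time | 0.5 | 2 | 0.2 | 95.9% | 2.00 SD |
| Group-by-time | 0.25 | 4 | 0.7 | 96.7% | 1.15 SD |
| Group-by-time | 0.25 | 2 | 0.8 | 95.9% | 1.0 SD |

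**5. What a 0.5 SD benefit means in the four-visit ANOVA.** Section E schedules "Part 3. Distribution of knee brace (available to treatment arm) post-operative 2 to 4 week recovery", so the brace cannot act at the pre-operative visit. A 0.5 SD benefit at the three follow-ups gives:
- between-group f = (0.5 × 3/4)/2 = 0.1875;
- group-by-time f = 0.25 × √3/4 = 0.108.

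Power with 24 patients:

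| Assumed ρ | 0 | 0.3 | 0.5 | 0.7 | 0.8 | 0.9 |
|---|---|---|---|---|---|---|
| Group-by-time | 12.0% | 15.4% | 20.2% | 32.0% | 46.5% | 78.8% |
| Between-group | 42.0% | 24.7% | 19.9% | 17.0% | 15.9% | 15.0% |

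Group-by-time reaches 95% only at a correlation of about 0.94 (0.92 with 30 patients).

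**The case against.** The protocol never says that 0.5 is Cohen's d or that one visit is compared. It plans ANOVA over four time points, where f is the usual metric, and several repeated-measures settings return 24 in total. A further one comes close. With f = 0.5, four visits and λ = f²·N·(m − 1) for group-by-time, 24 patients give λ = 0.25 × 24 × 3 = 18 and 94.7% power, with no correlation to enter; a strict 95% target needs 26. On this view the paragraph is under-reported rather than wrong, and some of the detail may sit in an SAP.

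Much of this stands. The figures of 105 per group and 21.6% hold only for the single-visit, 0.5 SD reading, and the number 12 is not shown to be a computing error. The tables above also rest on assumed correlations and a constant post-operative shift.

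It does not rescue the sentence. Each reconciling setting needs choices that the protocol does not state, and those in the first table aim at 1 SD or more. In the 94.7% convention the correlation is absorbed into f. Equating its λ with that in step 3 gives an implied shift of 2.0 × √(1 − ρ) SD: 1.41 SD at ρ = 0.5, and below 1 SD only when ρ exceeds 0.75. Nor can an SAP repair it, because the protocol itself states the power, the effect size and the resulting enrolment as a completed calculation.

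**Conclusion.** The concern holds. The stated inputs do not determine 12 per group, and the plain readings give something else: 105 per group (two-sided) or 88 (one-sided) for d = 0.5 at one visit, 27 per group for f = 0.5, and 36 or 12 in total for the four-visit ANOVA at f = 0.5 with an assumed correlation of 0.5.

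If the target is 0.5 SD at one visit, the chance of missing it (two-sided) is about 78% with 24 evaluable patients (100 − 21.6) and 74% with all 30 (100 − 26.2), against the 5% that the sentence implies. For a 0.5 SD benefit at all three follow-ups, neither ANOVA effect reaches 95% with 24 patients at any of the correlations computed from 0 to 0.9. These repeated-measures figures assume compound symmetry, no baseline difference and the noncentrality formulas given; another convention would shift them.

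The 95% claim should not remain as written, since the enrolment of 30 rests on it.

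**What to change.** Withdraw the 95% power sentence and restate power for one named primary endpoint and the planned test. State the effect-size metric (d or f), the sidedness, the number of visits, the correlation and where 0.5 comes from.

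- If a 0.5 SD difference at one visit is meant, suitable wording is: *With 12 evaluable patients per group (two-sided alpha 0.05, two-sample comparison), power is about 22% for a standardised difference of 0.5; 95% power is reached only at about 1.5 SD.*
- If a repeated-measures procedure was used, give its f, correlation, number of visits and tested effect (between-group or group-by-time), and the SD difference that this f implies.

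The cost is one reworded paragraph and one recalculation. No extra patients are needed, but the power quoted may be less favourable.
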